2.8.4.2 Vital signs

Vital signs tests performed includes the following:

- Sitting systolic blood pressure(SSBP) (mmHg)
- Sitting diastolic blood pressure(SDBP) (mmHg)
- Pulse rate (beats/min)
- Body weight (kg)

These parameters will be summarized by visit with standard summary statistics (mean, median, standard deviation, min, max), including changes from baseline. Change from baseline will only be summarized for subjects with both baseline and post-baseline values and will be calculated as defined in section 2.1.1 i.e. General definations.

The number and percentage of subjects with clinically notable vital signs changes from baseline will also be presented. Clinically notable vital sign results are provided in Table 2 below.

Vital Sign (unit)	Clinically notable criteria
Weight (kg)	decrease > 7% from Baseline
	increase > 7% from Baseline
Sitting systolic blood pressure (mmHg)	<90 and decrease from baseline of >20
	>180 and increase from baseline of >20
Sitting diastolic blood pressure (mmHg)	<50 and decrease from baseline of >15
	>105 and increase from baseline of >15
Pulse (bpm)	<50 and decrease from baseline of > 15
	>120 and increase from baseline of >15

 Table 2
 Clinically notable changes in vital signs

2.8.4.3 NYHA Class assessment

Patients NYHA class will be assessed at Baseline, at month 3, at month 6 and at month 12. At baseline, only patients with heart failure NYHA class II or III can be enrolled in the study. The total number and percentage of patient with each NYHA class will be provided by visits based

Novartis	For business use only	Page 18
SAP		PARASAIL / LCZ696BCA02

FAS. The change in NYHA class at month 3, 6 and 12 each compared to baseline (Day 1) will be summarized by frequesncy distribution.

2.9 Pharmacokinetic endpoints

Not applicable

2.10 PD and PK/PD analyses

Not applicable

2.11 6 MWT analysis

6 MWT data will be summarized for visit 1 (baseline), visit 5 (month 6) and visit 6 (month 12). Descriptive summary statistics (mean, median, standard deviation, min and max) for the baseline and change from baseline to visit 5 and visit 6 will be presented based on the total distance each patient walks in six minutes. The descriptive summaries will be presented by visit. Change from baseline will only be summarized for subjects with both baseline and post-baseline values and will be calculated as defined in section 2.1.1.

The 6 MWT analysis will be summarized based on the FAS. For the patients with two six minute walk test, best of the results based on longest distance covered will be considered for analysis.

The observations with total distance walked > 1000m will be excluded from the analysis as confirmed by the sites and CTT due to erroneous data entry.

2.13 Biomarkers

Not applicable

2.15 Interim analysis

An interim analysis may be performed after 50 patients have reached 12 weeks of treatment, and at any

time during the study as long as it does not impact the study completion.

3 Sample size calculation

The primary outcome measure for the current study will be the proportion of patients on 97 mg sacubitril / 103 mg valsartan bid of LCZ696 at 6 months of treatment. The data from clinical trials have shown that at 12 weeks (3 months) approximately 80% of patients have achieved this dose. In this current real – life study of 6 months (primary endpoint) a reasonable estimate of patients achieving this dose would be 70%.

Given that this is a single cohort, prospective study in which all patients are receiving the same treatment and the objective is to describe the proportion of patients reaching 97 mg sacubitril / 103 mg valsartan bid LCZ696, sample size requirements are based on the precision of the estimate. This is assessed with the 95% confidence interval. A reasonable level of precision is one with a 95% confidence interval width (ω) that is between 5 and 15% of the point estimate. With 300 patients enrolled in the study, the 95% Confidence Interval width will be \pm 5.2% which is equivalent to 7.4% of the point estimate of 70%, with upper and lower limits of 64.8% – 75.2% respectively. This is within the limits of reasonable precision.

4 Change to protocol specified analyses

Not applicable.

5 Appendix

5.1 Imputation rules

5.1.1 Study drug

If the date of an event is not known or is incomplete, the imputation rules are:

- a) If the day of the event is unknown, then the 15th day of this month will be imputed for a missing day;
- b) If only the month is unknown, then July will be used for imputation of the missing;
- c) If only the year of the event is known, then the 1st of July will be imputed for a missing day and month;
- d) The above rules are only for general case. If there is additional information available for the missing date, then the information should be used and the imputation of missing date should be treated differently. For example, if an event occurs between two visits and its date is missing, then the date in the middle of these visits may be used.

5.1.2 AE date imputation

AE date imputation is based only on a comparison of the partial AE start date to the treatment start date as mentioned in the Table 1-2 below.

- 1. If the AE start date year value is missing, the date uncertainty is too high to impute a rational date. Therefore, if the AE year value is missing, the imputed AE start date is set to NULL.
- 2. If the AE start date year value is less than the treatment start date year value, the AE started before treatment. Therefore:
 - a. If the AE year is less than the treatment year and the AE month is missing, the imputed AE start date is set to the mid year point (01JulYYYY).
 - b. Else if the AE year is less than the treatment year and the AE month is not missing, the imputed AE start date is set to the mid month point (15MONYYYY).
- 3. If the AE start date year value is greater than the treatment start date year value, the AE started after treatment. Therefore:
 - a. If the AE year is greater than the treatment year and the AE month is missing, the imputed AE start date is set to the year start point (01JanYYYY).
 - b. Else if the AE year is greater than the treatment year and the AE month is not missing, the imputed AE start date is set to the month start point (01MONYYY).
- 4. If the AE start date year value is equal to the treatment start date year value:
 - a. And the AE month is missing or the AE month is equal to the treatment start month, the imputed AE start date is set to one day after treatment start.
 - b. Else if the AE month is less than the treatment start month, the imputed AE start date is set to the mid month point (15MONYYYY).

c. Else if the AE month is greater than the treatment start month, the imputed AE start date is set to the start month point (01MONYYYY).

Table 1-2 AE date imputation

	MON	MON CEM	MON CEM	MONY CEN	
	MISSING	MON < CFM	MON = CFM	MON > CFM	
YYYY MISSING	NULL	NULL	NULL	NULL	
	Uncertain	Uncertain	Uncertain	Uncertain	
YYYY < CFY	(D) = 01JULYYYY	(C)= 15MONYYYY	(C)= 15MONYYYY	(C)= 15MONYYYY	
	Before Treatment Start	Before Treatment Start	Before Treatment Start	Before Treatment Start	
YYYY = CFY	(B)=TRTSTD+1	(C)= 15MONYYYY	(A)= TRTSTD+1	(A)= 01MONYYYY	
	Uncertain	Before Treatment Start	Uncertain	After Treatment Start	
YYYY> CFY	(E)= 01JANYYYY	(A)= 01MONYYYY	(A)= 01MONYYYY	(A)= 01MONYYYY	
	After Treatment Start	After Treatment Start	After Treatment Start	After Treatment Start	
Before Trea	tment Start	Partial indicates date prior to Treatment Start Date			
After Treatr	nent Start	Partial indicates date after Treatment Start Date			
Uncertain		Partial insufficient to determine relationship to Treatment Start Date			
LEGEND:					
(A)		MAX(01MONYYYY,TRTSTD+1)			
(B)		TRTSTD+1			
(C)		15MONYYYY			
(D)		01JULYYYY			
(E)		01JANYYYY			

5.1.3 Concomitant medication date imputation

Date imputation for concomitant medications will be imputed according to Novartis conventions described in [RAP Module 8].

Concomitant medication(CMD) start date imputation (#IMPUTMED)

Rules for imputing the CMD start date:

This algorithm is used when event is the partial start date of the concomitant medication, nondrug therapy/procedure, or prior anti-neoplastic therapy.

The following table explains the notation used in the logic matrix. Please note that **missing start dates** will not be imputed.

	Day	Month	Year
Partial CM Start Date	Not used	MON	YYYY

Novartis	For business use only	Page 23
SAP		PARASAIL / LCZ696BCA02

Treatment Start Date(TRTSDT)	Not used	TRTM	TRTY
------------------------------	----------	------	------

The following matrix explains the logic behind the imputation.

	MON	MON <trtm< th="">MON=TRTM	MON>TRTM	</trtm<>	MON=TRTM	MON>TRTM
	MISSING			
YYYY	(C2)	(C1)	(C1)	(C1)
	Uncertain	Uncertain	Uncertain	Uncertain
MISSING				
YYYY <trty< td="">(D)	(A)	(A)	(A)	</trty<>	(D)	(A)	(A)	(A)
	Before Treatment Start	Before Treatment Start	Before Treatment Start	Before Treatment Start
VVVV=TRTV	(C2)	(A)	(C1)	(B)
	Uncertain	Before Treatment Start	Uncertain	After Treatment Start
VVVV>TRTV	(E)	(B)	(B)	(B)
	After Treatment Start	After Treatment Start	After Treatment Start	After Treatment Start

The following table is the legend to the logic matrix.

Relationship	
Before Treatment Start	Partial date indicates CMD start date prior to Treatment Start Date
After Treatment Start	Partial date indicates CMD start date after Treatment Start Date
Uncertain	Partial date insufficient to determine relationship of CMD start date relative to Treatment
	Start Date
Imputation Calculation	
(A)	15MONYYYY
(B)	01MONYYYY
(C1 or C2)	IF relative reference start = before treatment start THEN TRTSDT-1
	ELSE IF relative reference start = ' ' THEN TRTSDT+1
(D)	01JULYYYY

(E)

01JANYYYY

Concomitant medication end date imputation

If not ongoing then -

If the CM end date year value is missing, the date uncertainty is too high to impute a rational date. Therefore, if the CM end year value is missing or ongoing, the imputed CM end date is set to NULL.

Else, if the CM end date month is missing, the imputed end date should be set to the earliest of the (treatment follow up period date, 31DECYYYY, date of death).

If the CM end date day is missing, the imputed end date should be set to the earliest of the (treatment follow up period date, last day of the month, date of death).

If the imputed CM end date is less than the existing CM start date, use the CM start date as the imputed CM end date

Concomitant medication date flag

If not a complete date then

Y - If year of the imputed date is not equal to YYYY else

M - If month of the imputed date is not equal to MON else

D

5.1.3.1 **Prior therapies date imputation**

As explained above in the section 5.1.3.

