## 5.5.5 Instructions for prescribing and taking study treatment

During the baseline visit all patients will be instructed to stop taking their ACEIs for 36 hours prior to taking the first dose of LCZ696. Patient receiving an ARBs will only have to discontinue their medication and start LCZ696 at the next schedule time. All patients will be initiated on LCZ696 at 24 mg sacubitril / 26 mg valsartan that can be up-titrated to LCZ696 49 mg sacubitril / 51 mg valsartan bid after 2-4 weeks and then up-titrated again to 97 mg sacubitril / 103 mg valsartan bid after another 2 – 4 weeks. Timing of LCZ696 up-titration will be dependent on patient tolerability and the judgement of the physician.

If patients experience any lack of tolerability including but not limited to hypotension and hyperkalemia, the dose of LCZ696 may be reduced or treatment suspended or terminated as per the judgement of the treating physician.

All dosages prescribed and dispensed to the patient and all dose changes during the study must be recorded on the Dosage Administration Record CRF.

The investigator should promote compliance by instructing the patient to take the study treatment exactly as prescribed and by stating that compliance is necessary for the patient's safety and the validity of the study. The patient should be instructed to contact the investigator if he/she is unable for any reason to take the LCZ696 as prescribed.

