5.1.3.2 Post therapies date imputation

As explained above in the section 5.1.3.

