EXCL09	History of malignancy of organ system (other than local basal cell carcinoma of skin), treated or untreated, within the past 5 years, regardless there is evidence	Excluded from PPS	4
EXCL10	Pregnant or nursing (lactating) women, where pregnancy is defined as the state of a female after conception and until the termination of gestation, confirmed by a positive hCG laboratory test.	Excluded from PPS	4

EXCL11	Women of childbearing potential, defined as all women physiologically capable of becoming pregnant, unless they are using effective methods of contraception during dosing of study treatment	Excluded from PPS	4
WITH01	Patient become pregnant, while taking study medication.	Excluded from PPS	0
WITH02	Due to the potential risk of angioedema when used concomitantly with an ACEI, LCZ696 is started within 36 hours without discontinuation of ACEI therapy.	Excluded from PPS	4
OTH01	Pregnancy test not performed as required per protocol	Excluded from PPS	0
OTH02	Pregnancy not reported within 24 hrs to Novartis while patient is on study treatment	Excluded from PPS	4
OTH03	Approved ICF update available but patient has not signed this version		
TRT01	Treatment with ARBs is not discontinued prior to intiation of study treatment	Excluded from PPS	4

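### Incomplete dates of prior and post therapies are imputed without regard to the first and last LCZ696 dose, so a drug known to lie outside treatment can be classed as concomitant

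*SAP*

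**What the plan says.** **End dates.** SAP 5.1.3 has two rules for a medication that is not ongoing. With the day missing, the end date is "set to the earliest of the (treatment follow up period date, last day of the month, date of death". With the month missing, it is "set to the earliest of the (treatment follow up period date, 31DECYYYY, date of death". The only further adjustment uses the drug's own start date: "If the imputed CM end date is less than the existing CM start date, use the CM start date as the imputed CM end date".

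**Start dates.** The matrix in the same section places a partial start date against the LCZ696 start (TRTSDT) only. One category in its legend reads "Partial date indicates CMD start date after Treatment Start Date", and the imputed value is then the first of the month or of the year. Where the order is uncertain, a relative-reference flag decides: TRTSDT-1 if the flag says the drug began before treatment, and otherwise "ELSE IF relative reference start = ' ' THEN TRTSDT+1".

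**Prior and post therapies.** Sections 5.1.3.1 and 5.1.3.2 each consist of a pointer: "As explained above in the section 5.1.3".

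**Use.** SAP 2.4.2 identifies concomitant medication from recorded or imputed start and end dates, and summarizes cardiovascular medication separately.

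**The switch.** Protocol 4.1 requires a stable ACEI or ARB at entry. For ACEIs, Protocol 5.5.5 says: "During the baseline visit all patients will be instructed to stop taking their ACEIs for 36 hours prior to taking the first dose of LCZ696". The same section, and the text after Protocol 5.1.2, let LCZ696 take the place of an ARB at its next scheduled dose.

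**The concern.** The rules are reasonable for a drug whose relation to study treatment is unknown. They fit badly when the relation is known. A prior therapy ended before LCZ696, and a post therapy began after it. Yet the end rule pushes the first forward to the latest possible date without looking at the LCZ696 start, and the start rule pulls the second back without looking at the last LCZ696 dose. A record known to lie outside treatment can then receive dates that make it concomitant.

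This trial is exposed because every eligible patient has an ACEI or ARB that ends at the switch, so stop and start nearly always fall in the same month. What is at stake is the accuracy of the cardiovascular concomitant-medication summary. For ACEIs in particular, an apparent overlap would draw a safety reader's attention, because the protocol gives angioedema as the reason for the 36-hour interval.

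**Working it through.** The documents give no figure on this point, so there is none to reproduce. The check applies the written rules to the calendar.

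**Inputs**
- Imputed end: month end (day missing) or 31 December (month missing), from SAP 5.1.3. The caps at follow-up or death cannot move the date before the first dose.
- Imputed start of a post therapy: first of the month (day missing). With the month missing it is TRTSDT+1 in the treatment-start year if the flag is blank, and 1 January in a later year. From SAP 5.1.3 through 5.1.3.2.
- Gap from stop to first LCZ696 dose: 1 to 2 calendar days for an ACEI (36 hours), 0 to 1 day for an ARB (next scheduled dose).
- Assumed: each day of a two-year window (July 2016 to June 2018) is equally likely; restart gaps of 1 to 30 days; 90 to 365 days on LCZ696.

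**Stop at the switch, day missing.** With gap g, the imputed end misses treatment only if the drug was stopped in the last g days of a month. Share affected = 1 − 12g/365.
- g = 0: 100%
- g = 1: 1 − 12/365 = 96.7%
- g = 2: 1 − 24/365 = 93.4%

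At g = 0 the true dates already share a day. With the month missing, the shares for the three gaps are 100%, 99.7% and 99.5%.

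*Example.* ACEI stopped 10 March, LCZ696 from 12 March. An end date recorded as March becomes 31 March, which gives 31 − 12 + 1 = 20 days of apparent co-treatment.

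**Therapy begun after the last dose, day missing.** The imputed first of the month falls on or before the last dose unless the therapy began within the first g days of a month. The share is again 1 − 12g/365 for gaps shorter than a month. At g = 30 only a start on the 31st qualifies, which is 7 days a year.

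| Gap after last dose | Share placed on treatment |
|---|---|
| 1 day | 96.7% |
| 2 days | 93.4% |
| 7 days | 1 − 84/365 = 77.0% |
| 14 days | 1 − 168/365 = 54.0% |
| 30 days | 7/365 = 1.9% |

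With the month missing and the flag blank, the share is 91.8% to 99.7% over these gaps.

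*Example.* LCZ696 from 12 March to 20 September, ACEI restarted 22 September. A start recorded as September becomes 1 September (20 days of apparent overlap). A start with only the year becomes 13 March (192 days).

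**After the fix.** With the end capped at TRTSDT-1 and the post-therapy start floored at last dose + 1, the artificial overlap is 0 days in every case above. Complete dates that truly overlap still show.

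**The case against.** The strongest reply is that the effect needs an incomplete date, and the documents report none. The ACEI/ARB end date is set by an instruction at the baseline visit of a prospective study. Heart-failure treatments are collected at that visit (Protocol Table 6-1), entries pass automatic checks (Protocol 8.2), and data are reviewed for completeness and queried (Protocol 8.3). This stands: the percentages above are conditional on a missing day or month and do not measure how often that happens here.

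A second reply is that the latest plausible end date is deliberately cautious and avoids hiding real exposure. That also stands where the order is unknown. It does not answer the case where the record shows the order. SAP 5.1.3 already uses such information for start dates through the relative-reference flag, but has no counterpart for end dates. The SAP clause telling the analyst to use additional information stands under 5.1.1 (study drug) and is not repeated in 5.1.3.

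Third, 5.1.3 refers to a sponsor convention (RAP Module 8) that is not available here, and SAP 2.4.2 does not spell out the overlap definition of concomitant. The written algorithm is taken as the rule.

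Two stronger readings are tempting. A reader might infer that compliant patients would leave the per-protocol set, because deviations WITH02 (ACEI) and TRT01 ("Treatment with ARBs is not discontinued prior to" LCZ696 starts) exclude from it. SAP 5.5 does not say that these deviations are derived from imputed dates, so no such effect is shown. A reader might also infer that any ACEI or ARB overlap would display a combination barred for angioedema. The protocol gives that reason for ACEIs only; an ARB needs no washout.

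**Conclusion.** The gap in the SAP is real, and the point is minor. Prior and post therapies are sent to rules that ignore the first LCZ696 dose for end dates and the last dose for start dates. Given a missing day, an ACEI or ARB stopped for the switch is imputed onto treatment in about 93% to 100% of calendar positions. For a therapy begun afterwards the share depends strongly on the gap: about 93% at 2 days, 54% at 14 and 2% at 30. The TRTSDT+1 result further needs a missing month in the treatment-start year (or a missing day in the treatment-start month) and a blank flag.

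The number of affected patients is unknown. Purely as an assumption, if 2% to 5% of 300 patients had an ACEI/ARB end date with the day missing, that is 6 to 15 records, and nearly all would be shown as concomitant. With complete dates throughout, the effect is nil.

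The consequence is confined to the concomitant-medication summaries and listings. No planned output reports days of overlap, so the durations above only illustrate the mechanism. The primary endpoint does not depend on these dates.

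**What to change.** 1. In SAP 5.1.3 and 5.1.3.1: where the record shows that the drug ended before the first LCZ696 dose, add TRTSDT-1 to the dates from which the earliest is taken for an incomplete end date. This mirrors the relative-reference rule for start dates.
2. In SAP 5.1.3.2: where the record shows that the therapy began after LCZ696 was stopped, set an incomplete start date to the later of the first of the month (or year) and last LCZ696 dose + 1.
3. Where the order is not recorded, keep the current rule.
4. Flag all imputed ACEI/ARB dates in a listing.

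The cost is a few sentences in the SAP, small program changes and one listing. The sponsor should confirm which data field shows the order, since the documents describe no specific field for a drug stopped because of the switch. Without one, step 3 applies. A capped end date serves only to classify the drug as prior; it is not evidence about the 36-hour interval.

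The downside is that a true overlap behind an incomplete date is no longer assumed in the table, but the record stays visible in the listing.

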5.1.3.2 Post therapies date imputation

As explained above in the section 5.1.3.

5.2 AEs coding/grading

NA

5.3 Laboratory parameters derivations

Clinically notable laboratory values

Clinically notable laboratory abnormalities for selected tests based on a percent change from baseline:

Hematology

RBC count	>50% increase, >20% decrease
Hemoglobin	>50% increase, >20% decrease
Hematocrit	>50% increase, >20% decrease
WBC count	>50% increase, >50% decrease
Platelet count	>75% increase, >50% decrease
Blood Chemistry	
ALT (SGPT)	>150% increase
AST (SGOT)	>150% increase
BUN	>50% increase
Creatinine	>50% increase
Total bilirubin	>100% increase
СРК	>300% increase
Alkaline phosphatase	>100% increase
Potassium	>20% increase, >20% decrease
Chloride	>10% increase, >10% decrease
Calcium	>10% increase, >10% decrease
Uric acid	>50% increase

5.4 Statistical models

5.4.1 Primary anlysis

For the proportion and percentage along with 95% confidence limits estimated using normal approximation (binomial proportion), statistical programmer may use the following code:

```
<Sample code>
proc freq data= <xxx>;
tables <xxx> / binomial;
run;
```

5.4.2 Secondary anlysis

For Incidence density rate for the number of dose reduction, following code may be used:

```
<Sample code>
proc genmod data=mydata;
model ndt =/dist=poisson link=log obstats; /* where ndt is the number of down
titrations for each of the patients.*/
```

run;

For Kaplan-Meier estimates of the probability of reaching LCZ 200 mg, following code may be used:

```
ods listing close;
proc lifetest data = <xxx> outsurv = <xxx> ;
    time TIME*censor(0);
    ods output productlimitestimates = res;
    ods output HomTests=pvalue;
    ods output Quartiles=med;
run;
ods listing;
```

